7.1.2 Secondary study parameters/endpoints

- Effects on oxygenation defined by the SpO₂
- Days under the oxygen support device
- Total amount of time the patient remains in the prone position
- Related serious adverse events. The following will be considered serious adverse events:
 - Oxygen desaturations (SpO₂ <90%)
 - Episodes of hemodynamic instability (BPsys < 90mmHg or BPsys drop > 10mmHg if BPsys < 90 before the maneuver)
 - Need of orotracheal intubation
 - o Cardiac arrest
 - o Displacement of the non-invasive respiratory support device
 - o Removal of central venous line, if documented
 - o Displacement of an arterial line, if documented
 - o Displacement of a urinary catheter, if documented
- Respiratory rate
- Dyspnea defined according to the Borg dyspnea scale (APPENDIX iv)
- ICU-free days and hospital-free days at day 90
- Mortality at day 28 and day 90

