6. STUDY POPULATION

6.1 Population (base)

We intend to recruit acute hypoxemic respiratory failure patients with a respiratory rate of more than 25 breaths per minute, $SpO_2 < 94\%$ and FiO_2 of at least 40% or more by either Venturi facemask, HFNC, or NIV/CPAP and, absence of decompensated respiratory acidosis during two years. Currently, we expect about 35 centers to participate in the trial.

Demographic data and clinical characteristics on screened patients, regardless of enrolment criteria match, will be recorded (registry). We will randomize 714 patients admitted to the participating centers' intensive care units and expect each participating center to randomize at least 25 patients who meet all inclusion criteria.

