7.2.2 Prone position

Supine to Prone

The patient will be placed in the prone position for at least 2 hours, which may be prolonged if the patient is comfortable or interrupted if the patient presents any criteria for prone position discontinuation (APPENDIX iii).

During the maneuver, FiO_2 will be increased by 25% above the baseline and then gradually decreased to the baseline value within the first 10 minutes of prone positioning, targeting for a SpO₂ of 94-96%. The total time of the prone position will be recorded.

The maneuver will be performed by two operators and the attending physician, while in patients with impaired mobility, up to 5 operators will be required. Skin protections will be used to avoid pressure sores. Also, the application of cushions will enhance patient tolerance to the

maneuver.

Arms can be at the side, in swimmer position, and can be moved to the patient's comfort. Vitals, SpO₂, and SpO₂/FiO₂ will be measured before and at the end of the prone position session.

Enteral or oral feeding will be interrupted 1 hour before prone positioning and re-established when the patient is in the semi-recumbent supine position.

Opiates, benzodiazepines, or alpha-2-adrenoceptor agonists can be used during the maneuvering at non-sedative doses to enable adaptation to the maneuver or treat anxiety symptoms related to respiratory failure.

If non-tolerance to the prone position, all clinical data will be collected, and the patients will be promptly rotated in the supine position. The reasons for prematurely unproning the patient will be accurately recorded. In case of sudden worsening of the oxygenation impairment or hemodynamics, 100% FiO₂ will be set, and the patient will be promptly positioned in the supine semi-recumbent position.

Prone to Supine

After the prone position period, the patient will be rotated to the semi-recumbent supine position for at least 2 hours and a maximum of 4 hours. This 2-hour time frame will depend on nursing availability, need for hygiene, complementary explorations, or diet.

As described previously, for the procedure, FiO_2 will be increased up to 25% above the baseline and then gradually decreased to the baseline value within the following 10 minutes targeting a SpO₂ of 94-96%.

Vitals, SpO_{2} , and SpO_{2}/FiO_{2} will be measured before and at the end of the supine position session.

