7.2.3 Standard management

The standard management of patients with acute hypoxemic respiratory failure will be done according to the usual practices of each participating center.

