7.2.4 Data to be collected

The documentation of the data will adhere to the timetable in APPENDIX v.

Pre-randomization variables

Pre-randomization variables will be collected:

- Gender and age; female + years
- Height and weight; kg + cm
- Date and time of hospital admission
- Source of admission to the ICU (emergency department, hospital ward, transfer from another ICU, transfer from a non-ICU ward of another hospital)
- Date and time of ICU admission
- Type of non-invasive respiratory support (HFNC, NIV, CPAP)
- COPD with inhalation therapy and/or steroids
- Smoking status; never, former (at least three months prior) or current
- History of active cancer; if yes, specify the type of cancer
- History of diabetes mellitus; oral medication or insulin therapy
- History of hypertension
- Use of angiotensin-converting enzyme inhibitor
- Use of angiotensin II receptor blocker
- Use of statins
- Actual organ function evaluation
 - Respiratory rate
 - SpO₂; %
 - SpO₂/FiO₂
 - ROX index; SpO₂/FiO₂: RR
 - Dyspnea defined according to Borg dyspnea scale
 - Chest X-ray

- Non-invasive mean arterial pressure; mmHg
- Heart rate; BPM
- Body temperature; °C
- BUN, Creatinine, AST, ALT, Bilirubin, Hemoglobin, Platelets, PTT, WBC count
- SOFA score
- APACHE II, SAPS II; any of those used by the participating center

Post-randomization variables

One hour before each position change (supine and prone), the following variables will be collected for the duration of the protocol, which will be for 48 hours (APPENDIX v):

- Organ function evaluation:
 - Respiratory rate
 - SpO₂; %
 - SpO₂/FiO₂
 - ROX index; SpO₂/FiO₂: RR
 - Dyspnea defined according to the Borg dyspnea scale (APPENDIX v)
 - Non-invasive mean arterial pressure; mmHg
 - Heart rate; BPM
- Non-invasive support device parameters:
 - HFNC: flow; liters/min. FiO₂; %
 - CPAP: PEEP; cmH₂O. Flow; liters/min; Tidal volume; ml. FiO₂; %
 - NIV: PEEP; cmH₂O. Pressure support over PEEP; cmH₂O. Flow; liters/min. Tidal volume; ml. FiO₂; %
- Complications possibly related to prone position:
 - New hypotension (BPsys < 90mmHg or BPsys drop > 10mmHg, if BPsys < 90 before the maneuver)
 - New bradycardia (HR <50bpm or HR drop > 20%, if HR < 50 before the maneuver)
 - New hypoxemia (SpO₂ ≤ 90% or SpO₂ drop > 5%, if SpO₂ < 90% before the maneuver)
 - Ulcers
 - Displacements of any of the following: respiratory support device, peripheral or venous central line, oro or nasogastric tube, urinary catheter

Post-protocol variables

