The statistical analysis will be based on the intention-to-treat principle. Besides, we will perform a per-protocol analysis to check for the robustness of the results. The intention-to-treat analysis includes all patients as randomized regardless of whether they received the randomized treatment or other protocol deviations. Per-protocol group analysis only considers those patients who completed the treatment according to the originally allocated protocol.

Data analyses will follow an a priori documented statistical analysis plan, which will be finalized before the end of data collection. By definition, only the analysis of the primary outcome is confirmatory; all other analyses are exploratory. The analysis strategy follows the intention-to-treat principle. The analysis will be undertaken blinded by a statistical expert. Statistical significance is considered to be at a p-value of 0.05, where 95% confidence levels will express appropriate statistical uncertainty.

The analysis will be performed with R statistics.

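### The oxygenation endpoint is SpO2 alone, but no common rule governs FiO2 in the two arms, so a between-arm SpO2 comparison can hide a gain that appears as a lower oxygen need

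*Protocol*

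**What the plan says.** **Endpoint.** Section 7.1.2 gives the oxygenation endpoint as "Effects on oxygenation defined by the SpO₂". It names neither FiO2 nor a time point.

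**Prone arm.** Under 7.2.2, FiO2 is raised by 25% for the turn and then "gradually decreased to the baseline value within the first 10 minutes of prone positioning, targeting for a SpO₂ of 94-96" percent. A similar step applies on the return to supine.

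**Control arm.** Under 7.2.3, standard management "will be done according to the usual practices of each participating center". No FiO2 rule or saturation target is stated.

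**Data collected.** Section 7.2.2 measures SpO2/FiO2 before and at the end of each prone and supine session. Section 7.2.4 lists SpO2, SpO2/FiO2 and "ROX index; SpO₂/FiO₂: RR" among the post-randomization variables, timed as follows: "One hour before each position change (supine and prone), the following variables will be collected for the duration of the protocol", which is 48 hours. Appendix v schedules SpO2 for randomized patients before the protocol starts and on Days 1 to 7; its rows do not list FiO2.

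**Status.** Section 8.2 states that "only the analysis of the primary outcome is confirmatory; all other analyses are exploratory".

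**The concern.** SpO2 is the quantity clinicians steer by and FiO2 is the control they turn. When FiO2 is adjusted toward a saturation, an improvement in gas exchange may show up mainly as a lower FiO2, with SpO2 much the same. A comparison of SpO2 between arms then reflects position and oxygen titration together. Randomization does not remove this, because FiO2 is set after allocation and the instructions for setting it are not the same in the two arms.

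At stake is a named objective of the trial (4.1 includes effects on oxygenation). If proning improves gas exchange, the named measure may fail to show it. The choice of variable is made in the protocol, so this is not simply a detail left to the statistical analysis plan.

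**Working it through.** The protocol gives no figure for this endpoint, so there is nothing of its own to reproduce. The check sets the sections side by side and then works one example.

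**1. Is FiO2 tied to a common rule?**
- Prone: back to baseline, with a target of 94-96% (7.2.2).
- Control: "according to the usual practices of each participating center" (7.2.3).
- Section 6.1 describes patients with SpO2 below 94% on FiO2 "of at least 40% or more by either Venturi facemask, HFNC, or NIV/CPAP". Such a patient starts below the prone arm's band. At the first turn, baseline FiO2 and the target can both hold only if SpO2 has risen, and the text does not say which prevails.

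So no written rule makes FiO2 the same in the two arms.

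**2. What can SpO2 miss?** The patients are assumed; only the return to baseline FiO2 comes from 7.2.2. Formula: ratio = SpO2 (%) / FiO2 (fraction).

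| | SpO2 | FiO2 | SpO2/FiO2 |
|---|---|---|---|
| Both at start | 92 | 0.50 | 92/0.50 = 184 |
| Prone, later | 95 | 0.50 | 95/0.50 = 190 |
| Control, later | 95 | 0.60 | 95/0.60 = 158.3 |

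- SpO2 difference: 95 - 95 = 0 points.
- Ratio difference: 190 - 158.3 = 31.7 in favor of prone.
- Control FiO2 0.55: 190 - 95/0.55 = 190 - 172.7 = 17.3.
- Control FiO2 0.70: 190 - 95/0.70 = 190 - 135.7 = 54.3.

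**3. Is the hidden difference real or made by the ratio?** Of the 31.7 points, 190 - 184 = 6 come from the prone patient's rise and 184 - 158.3 = 25.7 from the control's higher FiO2. Assuming a standard oxygen dissociation curve, the implied PaO2/FiO2 is about 128 at the start, 151 for the prone patient later and 126 for the control later. The lungs do differ at the end (151 - 126 = 25) although SpO2 is equal. The ratio points the right way. It also overstates the control's decline: 158.3/184 - 1 = -14%, against an implied PaO2/FiO2 that hardly moved (128 to 126).

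**4. When are readings available in both arms?** The 48-hour readings that include SpO2/FiO2 are tied to position changes, and 7.2.3 schedules none for controls. Appendix v gives SpO2 on Days 1 to 7 for all randomized patients, so common days do exist. Those rows carry SpO2 without FiO2, and the daily list under post-protocol variables in 7.2.4 does not name FiO2 either.

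**The case against.** The strongest reply is that little is lost. Only the primary analysis is confirmatory. SpO2/FiO2, ROX and device FiO2 are already on the 48-hour list, and an analysis plan may add an oxygenation index. The wording on position changes may also be meant for both arms, since 7.2.5 uses supine and prone to label the two groups. Within-patient SpO2 change across a session stays informative if FiO2 does return to baseline. All of this stands and keeps the priority low. What remains is that the protocol names SpO2 as the measure; choosing the ratio later would depart from the stated endpoint.

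Four stronger readings are tempting, and the documents do not support them:
- **That FiO2 differs between arms.** The protocol shows only that no common rule is written. It neither states nor estimates a difference.
- **That the arms share no reading times.** Appendix v schedules SpO2 on Days 1 to 7 without restricting it to one arm. The gap is the missing FiO2, and the text does not say whether Day 1 counts from randomization or from the end of the intervention.
- **That the wide range of FiO2 allowed at entry biases the comparison.** That is spread between patients, which randomization balances in expectation.
- **That SpO2 would show a false gain for proning.** This would need controls to be held at lower saturations, and nothing in the text says they are.

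It is also fair to object that SpO2/FiO2 is not free of titration effects, as step 3 of the working shows. It is a better measure, not a clean one.

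**Conclusion.** The point holds as a minor one. SpO2 alone is a weak measure for a between-arm oxygenation comparison when one arm has an FiO2 instruction with a saturation target and the other has neither. In the example, SpO2 shows a difference of 0 where SpO2/FiO2 shows 32 (range 17 to 54). This rests on assumed patients and an assumed control FiO2 of 0.60 (0.55 to 0.70). It shows that a gain can be hidden, not how often or by how much this would happen in the trial. The reading that the ratio in step 3 reflects a real difference also assumes a standard dissociation curve.

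The consequence is confined to one exploratory secondary endpoint. The primary endpoint, the sample size of 714 and the treatment of either arm are untouched.

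**What to change.** In 7.1.2, name SpO2/FiO2 as the oxygenation endpoint at times common to both arms, for example Day 1 and Day 2, or 24 and 48 hours after randomization. State where the day count starts. In Appendix v, record FiO2 with the SpO2 already scheduled on those days. Report SpO2 and FiO2 beside the ratio. Leave 7.2.2 and usual care in controls as they are.

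The cost is a reworded endpoint line and one extra FiO2 value per patient at each chosen time. The ratio still shifts somewhat with FiO2 titration and discriminates poorly at high SpO2, which is why its two components should be shown with it.

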7. METHODS

7.1 Study parameter/endpoints

7.1.1 Main study parameters/endpoint

• Rate of invasive mechanical ventilation during the first fourteen days of enrolment

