8.3 Data Safety Management Board (DSMB)

A DSMB will be installed to monitor safety and the overall conduct of the trial. The DSMB will compose of 5 individuals who will be invited, one of which will be the chairperson.

The DSMB will first convene after the first 100 patients, approximately 6 months after the first patient is enrolled.

- Subsequently, the DSMB will attend videoconferences every six months
- All adverse events will be reported to the DSMB for review. All serious events will be reported within 24 hours after being received by the coordinating center. Non-serious events will be reported within one week of reception by the coordinating center (APPENDIX vi).
- Adverse events possibly occurring during this study include but are not limited to unexpected death or cardiac arrest in either the control or treatment group (APPENDIX vi).

• The DSMB will monitor the overall status of the trial: number of patients enrolled overall and per each center, adherence to protocol overall and per center and results of the interim analysis.

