APPENDIX vi. ADVERSE EVENTS

1. Definitions

An adverse event (AE) is generally defined as any unfavorable and unintended diagnosis, symptom, sign (including an abnormal laboratory finding) syndrome or disease which either occurs during the study, having been absent at baseline, or if present at baseline, appears to worsen. Adverse events are to be recorded regardless of their relationship to the study intervention. With respect to intensity, adverse events are classified as follows:

- Mild some awareness of symptoms, but easily tolerated;
- Moderate symptoms causing enough discomfort to interfere with usual activity;
- Severe incapacitating event causing inability to work or to perform usual activity.

A Serious Adverse Event (SAE) is defined as any experience that suggests a significant hazard or side effect with respect to participants participating in a clinical study. This includes any experience which:

- is fatal or life threatening,
- is permanently disabling, i.e. incapacitating or interfering with the ability to resume normal life patterns,
- requires hospitalization or prolongation of hospitalization,
- requires other medically important circumstance (requires medical treatment to avoid one of the above mentioned conditions).

A special form of the SAE is the Suspected Unexpected Serious Adverse Reaction (SUSAR).

Adverse events possibly occurring during this study include but are not limited to unexpected death or cardiac arrest in either the control or treatment group.

2. Documentation of AEs and SAEs

All adverse events that occur between start of randomized intervention and 90-days follow up have to be immediately documented in the participant's electronic CRF. AEs are classified as either serious or non-serious. Details about the clinical symptoms, clinical course and if medical treated, about therapies used should be provided as well as information about relationship to

study intervention, overall intensity and outcome of the adverse event.

3. Reporting of Adverse Events

Reporting responsibilities of the local coordinator

Any AE occurring after start of randomized study intervention will be reported. The participant will be followed until remission of the symptoms. When reporting an AE/SAE, a clinical narrative on each AE/SAE should be added, which gives the clinical context of the event and allows the DSMB to carefully review the AE/SAEs.

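### The related-SAE endpoint in Section 7.1.2 conflicts with Appendix vi, counts intubation as harm, and does not compare the arms like with like

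*Protocol*

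**What the plan says.** Section 7.1.1 sets the primary endpoint: "Rate of invasive mechanical ventilation during the first fourteen days of enrolment".

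Section 7.1.2 introduces the safety endpoint with "Related serious adverse events. The following will be considered serious adverse events". Its list includes SpO2 below 90%, a hypotension item, "Need of orotracheal intubation", cardiac arrest, "Displacement of the non-invasive respiratory support device", removal or displacement of venous and arterial lines, and "Displacement of a urinary catheter, if documented". The hypotension item is partly defined by reference to a position change: "BPsys drop > 10mmHg if BPsys < 90 before the maneuver".

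Appendix vi defines an SAE by its consequences: death or threat to life, lasting disability, hospital admission or a longer stay, or medical importance. It also states: "Adverse events are to be recorded regardless of their relationship to the study intervention".

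Section 7.2.4 lists hypotension, hypoxemia and displacements again, as complications possibly related to proning. Section 8.3 adds a reporting rule: "All serious events will be reported within 24 hours after being received by the coordinating center". Under Section 7.2.3 the control arm receives whatever each centre ordinarily does.

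**The concern.** There are three problems.

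- **Two definitions of serious.** A displaced urinary catheter or a brief desaturation is an SAE under Section 7.1.2 but need not be one under Appendix vi. Sites cannot code the same event consistently from both.
- **A relatedness filter with no counterpart in the control arm.** The endpoint is restricted to related events, yet nothing says what a control event would be related to.
- **Efficacy counted as safety.** Intubation is in substance the primary outcome. In any total that includes it, a benefit on the primary outcome lowers the apparent harm of proning.

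At stake is whether the stated safety endpoint can show if awake proning carries harm that usual care does not.

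**Working it through.** **Definitions side by side**

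| Event | Section 7.1.2 | Section 7.2.4 | Appendix vi |
|---|---|---|---|
| Low SpO2 | SAE if below 90%, no rule for a low baseline | Complication if at or below 90%, or a drop of more than 5% when already below 90% | SAE only if a seriousness criterion is met |
| Urinary catheter displaced | SAE | Complication | SAE only if a seriousness criterion is met |
| Intubation | SAE | Not in the complications list | Would generally meet a seriousness criterion |
| Death | Not in the SAE list (mortality is a separate endpoint) | Not in the complications list | SAE |

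Section 5 describes patients entering with SpO2 below 94%, so some may already be under 90% at baseline. Section 7.1.2 has no rule for them.

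**If the relatedness filter is applied.** Appendix v ties the end-of-protocol adverse-event item to prone position. The hypotension item refers to a manoeuvre, and Section 7.2.4 times data collection to position changes. Appendix vi starts documentation at the start of the randomized intervention. None of these reference points is defined for a usual-care patient. Prone patients can score on the endpoint in ways that control patients cannot, so the comparison is asymmetric. Intubations judged to be disease progression would not count here.

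**If the filter is not applied and events are totalled.** Inputs from Section 6.4: 34% standard, 24% prone, two-sided 0.05, power 80%, 322 per group, 357 after 10% dropout.

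Plan's own figure first, with pooled variance and mean rate 0.29:

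n = [1.960 × √(2 × 0.29 × 0.71) + 0.842 × √(0.34 × 0.66 + 0.24 × 0.76)]² / 0.10² ≈ 322 (323 when rounded up).

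This agrees with the stated 322. Dropout gives 322 / 0.90 = 357.8, against 357 stated. The rates can therefore be used.

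Intubations expected at 357 per arm:

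- Standard: 0.34 × 357 = 121.4
- Prone: 0.24 × 357 = 85.7
- Sum 207.1; difference 35.7

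At 322 per arm the figures are 109.5 and 77.3, a difference of 32.2.

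**Patient-level illustration.** Let q be the proportion with any other listed event. The protocol gives no q, so 5% to 30% is an assumption, as is independence from intubation. Then any event = 1 − (1 − p)(1 − q), with p the intubation rate. The prone q that makes the arms equal is 1 − 0.66(1 − q)/0.76.

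| q | Standard, any event | Prone, any event (same q) | Gap (points) | Chance of p<0.05 | Prone q that hides the gap | Power to see that excess with intubation removed |
|---|---|---|---|---|---|---|
| 5% | 37.3% | 27.8% | 9.5 | 0.77 | 17.5% | >0.99 |
| 10% | 40.6% | 31.6% | 9.0 | 0.71 | 21.8% | 0.99 |
| 20% | 47.2% | 39.2% | 8.0 | 0.58 | 30.5% | 0.90 |
| 30% | 53.8% | 46.8% | 7.0 | 0.46 | 39.2% | 0.74 |

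Probabilities are for two-sided 0.05 at 357 per arm.

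**Sensitivity to overlap.** With no overlap the gap is (34 + q) − (24 + q) = 10 points. If every intubated patient also had another listed event, intubation would add nothing to the patient-level proportion, although it would still add 121 and 86 to an event count. Appendix ii makes sustained SpO2 below 90% one of its intubation criteria, so substantial overlap is likely and the table should not be read as a forecast.

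**The case against.** The strongest reply is that the protocol never defines a total or an any-SAE composite. Section 7.1.2 is a list of event types, and tabulation is commonly left to the SAP. Reported line by line, intubation merely repeats the primary result. This stands: a reader might infer that the plan prescribes a pooled count that conceals harm, and the text does not say so.

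The two distortions also cannot occur together. If the filter works, most of the 207 intubations drop out; if it does not, the asymmetry from relatedness disappears. That is correct, but each reading leaves a flawed comparison.

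Other tempting inferences are not supported:

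- *Relatedness is judged unblinded.* The protocol does not say who makes this judgement in relation to blinding. Section 7.2.1 provides a blinded outcome evaluator, and Appendix vi has an SAE manager judge the reports, with DSMB review.
- *A 10-point excess of harm would cancel exactly.* That needs no overlap between intubation and the other events, which Appendix ii makes implausible.
- *Safety cannot be assessed at all.* Appendix vi records events in both arms whatever their relationship, so the raw data should exist. That rule can coexist with a related-only endpoint; the firm contradiction is over seriousness.
- *All the displacements are minor.* Loss of respiratory support in these patients is not evidently minor. The mismatch with Appendix vi is clearest for the urinary catheter and brief desaturation.
- *Section 7.1.2 alone creates the 24-hour reports of intubation.* Intubation would generally qualify under Appendix vi as well. What Section 7.1.2 adds is the desaturations and displacements that are not otherwise serious.

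Finally, Section 8.2 treats everything except the primary analysis as exploratory, which limits the consequence.

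**Conclusion.** The concern holds as a defect in how the safety endpoint is defined. The conflict between Sections 7.1.2 and 7.2.4 and Appendix vi is plain in the text and rests on no assumption. So is the lack of any meaning for a related event in the control arm.

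The numerical effect is conditional. If relatedness is not applied and events are totalled, intubation contributes about 121 against 86 events, about 36 fewer with prone, at the planned rates. Under the assumed q and independence, the patient-level gap would be 7.0 to 9.5 points with no true safety difference, and a true excess of about 9 to 12.5 points in the other events could be masked. Overlap with desaturation could shrink intubation's contribution to that proportion to nothing. The primary analysis is not affected. An SAP could settle the tabulation, but it could not remove the conflict between protocol definitions that sites use for reporting.

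**What to change.** 1. Reconcile Sections 7.1.2 and 7.2.4 and Appendix vi to a single SAE definition, with one SpO2 limit and one baseline rule wherever the event is named.
2. Exclude intubation explicitly from any between-arm SAE total and report it as the efficacy outcome. The exclusion must be written out, because intubation would otherwise re-enter under the Appendix vi criteria. It may still be reported to the DSMB.
3. Label the other Section 7.1.2 items as prespecified events of interest, and report each separately.
4. Compare events by arm regardless of judged relatedness, counted from randomization in both arms, with ascertainment rules that do not depend on a position change. Relatedness can be kept as a descriptive field.

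The cost is rewording of the protocol and CRF. Appendix vi already requires events to be recorded whatever their relationship, so little or no new data collection should follow. Sample size and the primary analysis do not change.
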